v3.0	27 OCT 2021	Data management platform was changed to AirTable to increase security and ease of use. Option for study team to obtain verbal consent was added.
v4.0	30 NOV 2021	Broadened language to allow flexibility in testing frequency and time points based on evaluation of safety data (e.g. tertiary transmission) and feedback from the study safety committee and NCDHHS. Updated consent forms to reflect the protocol modifications.

PROTOCOL SYNOPSIS

Protocol Title:	Test to Stay in School: COVID-19 Testing Following Exposure in K-12 School Communities
NCT #	NCT05052580
Phase:	N/A, a prospective, interventional study
Objectives:	
Primary:
 
 1. Evaluate severe acute respiratory syndrome coronavirus 2 (SARS-CoV-2) transmission following exposure in Kindergarten through 12th grade schools. 
Secondary:
 
 1. Characterize the effect of individual-level mitigation practice (e.g., masking) on SARS-CoV-2 spread. 2. Characterize the effect of exposure setting on SARS-CoV-2 spread. 3. Describe COVID-19-related school absences for up to 14 days following within-school SARS-CoV-2 exposure.
Study Design:	
Participants in school communities who have been exposed to SARS-CoV-2 will be tested for COVID-19 on the day after exposure (day 1) and at days 3, 5, and 7 following initial known exposure. Data will be reviewed weekly by a study safety committee and NCDHHS, and updates to the testing protocol (test frequency and test time points) will be made based on analysis of data. Mitigation practices including masking, the context of exposure (classroom, school bus, after school sporting event, lunch, etc.), and results of COVID-19 test will be documented.

Study Population:	School communities
Number of Participants:	Up to 1,000,000
Number of Sites:	Single coordinating site
Duration of Study:	2 years

1 BACKGROUND INFORMATION AND RATIONALE

1.1 Background Information

1.1.1 COVID-19 and Kindergarten-12th grade school closures

Widespread Kindergarten through 12th grade school closures are the most important COVID-19-related threats to child health. Since February 2020, children have accounted for one-tenth of severe acute respiratory syndrome coronavirus 2 (SARS-CoV-2) cases; up to 2.2% and 0.04% of pediatric cases have resulted in hospitalization or death, respectively, and as many as 50% of cases are asymptomatic.^{1,2} However, children have been far from spared of the downstream effects of this pandemic. In March 2020, most Kindergarten through 12th grade schools preemptively closed to in-person education in an attempt to limit viral spread. Most publically-funded Kindergarten through 12th grade schools across the nation, responsible for educating >55 million of the nation's children, remained closed in the early 2020, citing concerns about viral transmission and risks to students and staff. Because public schools play such a vital role in the educational, social, and emotional development of young children as well as the delivery of vital services such as food and healthcare, it is not surprising that early data show food insecurity has doubled; 65% of children 9-13 years are less physically active; 1/6th of children have worsened behavioral health; suicidality may be increasing, and physical abuse is more severe.³⁻⁷ The potential consequences of these findings are deep and far-reaching; children with food insecurity are twice as likely to be in fair or poor health, more likely to be hospitalized, and more likely as adults to have poor job readiness. Chronic absenteeism in early primary school decreases the likelihood of reading at grade level by the third grade and increases the risk of drop out by 4 times compared to proficient readers.⁸ Adults with less than a high school education are 2.4 times as likely as high school graduates to rate their health as poor and live 10 years fewer than those with graduate education. Considering these profound impacts, access to in-person education is imperative.

In North Carolina (NC), schools have been able to show low secondary transmission of SARS-CoV-2 within school buildings.⁹ Data in school communities confirms that mitigation strategies such as proper masking have been imperative in reducing spread in schools.⁹⁻¹¹

Yet, current policies and procedures requiring quarantine after close contact exposures to limit further spread have led to hundreds of thousands of missed school days and have threatened the school workforce, greatly impeding school operations and the ability of children to appropriately learn. In the fourth quarter of 2021 in NC alone, more than 40,000 students and staff were required to quarantine as a result of being a close contact of a COVID-19 case (unpublished). Fortunately, recent CDC and local guidance have eliminated quarantines for most exposed, unvaccinated, asymptomatic children who are wearing a mask and who are in close contact with another masked, infected child within the classroom setting. However, many quarantines continue to result in unvaccinated adults, children exposed to infected adults, and masked exposures occurring outside of the classroom (e.g., athletics or busing). Moreover, schools and local governments are steadily lifting mask mandates, even as local community cases rise, contributing to exponential increases in quarantines that not only keep children and staff out of schools and parents out of work, but have often overwhelmed school resources and the public health system.

To address the issue of quarantines while ensuring that the school and surrounding community remain safe from SARS-CoV-2 spread, some locales have begun implementing a "test to stay strategy", whereby a close contact undergoes serial testing over a specified duration of time.

The close contact must wear a mask during this time period but is not required to undergo quarantine as long as the screening tests remain negative and the contact remains asymptomatic. While this strategy is supported by strong scientific premise and initial data are promising, the impact of this strategy on quarantine, and secondary and tertiary within-school transmission has not been systematically evaluated.

This study will partner with schools to allow students and staff to remain in school following exposure if they continue to test negative for COVID-19 over pre-determined intervals. This study aims to collect data to assess the spread of SARS-CoV-2 in school communities with varying mitigation strategies to provide data-backed guidelines for mitigation strategies in schools. The study team will work with NCDHHS and a safety monitoring team on a weekly basis to interpret data, evaluate safety, and design next steps (e.g. testing frequency and timing).

1.2 Scientific Rationale

This study will evaluate spread of SARS-CoV-2 following known exposure in schools. This information will be critical for determining future policies surrounding COVID-19 testing, quarantine, and mitigation practices in the Kindergarten through 12th grade school environment. Staff and students who participate in this study will provide consent for testing and collection of data on demographic factors, symptoms, quarantine, test results, and tertiary spread. The existing partnerships with schools established through the ABC Science Collaborative, a partnership between Duke and University of North Carolina (UNC) faculty and Kindergarten through 12th grade schools in NC, which was formed in the summer of 2020 will be leveraged.

This study will be conducted across multiple age groups of school-age children and staff, multiple educational settings, and multiple different educational cultures to increase the potential generalizability of study results. Additionally, this study aims to prospectively collect real-world data, which otherwise would be unavailable, to guide evidence-based decision- and policymaking surrounding transmission and quarantine.

1.3 Potential Benefits

Participants may benefit from COVID-19 testing, symptom screening, masking and early identification of COVID-19. Additionally, individuals may benefit from a broader understanding of appropriate mitigation strategies to reduce spread of SARS-CoV-2, reduced need for quarantine, and increased school attendance. For the school community, this study will permit students and staff to stay in school provided they test negative, minimizing disruption to school and home operations. The broader impact that data collection has on advancing the scientific understanding of COVID-19 and associated outcomes may benefit others in the future. Additionally, this study aims to prospectively collect real-world data, which otherwise would be unavailable, to guide evidence-based decision- and policymaking surrounding transmission and quarantine.

1.4 Known Potential Risks

Community-level risk(s): For school communities to participate in this protocol, there is a potential risk for increased exposure to SARS-CoV-2 from elimination of quarantine; however,

frequent testing, symptom screening and requirements for masking in a controlled environment are designed to minimize this risk to the community.

Individual-level risk(s): Risks associated with this study include risks associated with the COVID-19 testing procedure, specifically risks associated with lower nasal swab and the potential loss of confidentiality.

- **Potential Risks of Nasal Swabs:** Risks include mild irritation, insignificant local pain, and minor bleeding.
- **Potential Risk of Loss of Confidentiality:** There is a potential risk of loss of confidentiality. Every effort will be made to protect the participant's protected health information (PHI) as well as other identifying information, but this cannot be guaranteed.

2 OBJECTIVES AND OUTCOME MEASURES

	Objective	Endpoints
Primary:	Evaluate severe acute respiratory syndrome coronavirus 2 (SARS-CoV-2) transmission following exposure in Kindergarten through 12th grade schools.	
 Proportion and number of students with positive COVID-19 test following known exposure. Proportion and number of staff with positive COVID-19 tests following known exposure. Proportion and number of exposures undergoing the test-to-stay protocol that result in additional transmission. Time to test positivity among those exposed to SARS-CoV-2 and undergoing the test-to-stay protocol.
Secondary #1:	Characterize the effect of individual-level mitigation measures (e.g., masking) on SARS-CoV-2 spread.	
 Proportion and number of masked students with positive COVID-19 test who were exposed to SARS-CoV-2 from masked versus unmasked individuals. Proportion and number of masked staff with positive COVID-19 test who were exposed to SARS-CoV-2 from masked compared to unmasked individuals Proportion and number of unmasked students with positive COVID-19 tests who were exposed to SARS-CoV-2 from masked compared to unmasked individuals Proportion and number of unmasked staff with positive COVID-19 tests who were exposed to SARS-CoV-2 from masked compared to unmasked individuals
Secondary #2	Characterize the effect of exposure setting on SARS-CoV-2 spread.	
 Proportion and number of students with positive COVID-19 test after indoor vs. outdoor exposure. Proportion and number of students with positive COVID-19 test after athletic vs. classroom exposure. Proportion and number of students with positive COVID-19 test after bus vs. classroom exposure.
Secondary #3:	Describe COVID-19-related school absences for up to	
 Total number of school days missed due to symptoms after exposure.

	14 days following SARS-CoV-2 exposure.	
• Total number of school days missed due to isolation after positive COVID-19 test.• Total number of school days missed due to quarantine after SARS-CoV-2 exposure.
--	--	---

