5.3 Enrollment/Baseline

Participants or their parent/legal guardian will provide informed consent (or assent). Applicable informed consent from the participant or parent/legal guardian (and assent if applicable) for all participants will be documented. After consent, the participant will be assigned a unique ID by the school nurse or administrator. The school nurse or administrator will collect study-related variables via a spreadsheet using one of two different methods. The school nurse may use AirTable, a system designed by Technology and Data Solutions, or standard excel spreadsheets, which will be sent to the research team. The research team will have access to individual-level data but will not have access to names or other identifiers. While the study team will have access to the consents completed via REDCap, the team will not know which unique ID belongs to which individual.

The following information will be collected from the student at the time of enrollment. Information may be collected directly from the participant, their parent/legal guardian, or via a school nurse. The information will include the following:

- Participant demographics (age, sex, English proficiency, and vaccination status)
- Mitigation data collection including whether the participant was masked or unmasked, and vaccination status (if known)
- Exposure details include when exposure occurred, where it occurred, and if the individual who caused the exposure was masked or unmasked

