8.2.2 Secondary Analysis

The proportion and number of students/staff who reported masking and unmasking will be reported and presented in graphical form. The primary analysis will be repeated for masked and unmasked participants (students and staff) separately. The primary analysis will be repeated for masked and unmasked source of exposure separately.

School absences will be analyzed by absences due to symptoms, positive COVID-19 test, or due to quarantine for exposure to SARS-CoV-2. To account for the within-school correlation of outcomes, analyses will be conducted using a generalized estimating equations approach using a loglink suitable for count outcomes, with a working independence correlation structure.

To account for within-school correlation, a risk between the schools using a generalized estimating equation approach with an identity link and a working independence correlation structure will be estimated. The risk difference will be estimated for each semester during the study period, as well as overall. Students will be censored by end of data or study withdrawal. Censoring will be addressed by incorporating inverse-probability censoring weights into the regression model, with censoring risk estimated with a Kaplan-Meier estimator.

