1.3 Endpoints

Primary Endpoints:

- Proportion of students with positive COVID-19 test following known within-school exposure.
- Proportion of staff with positive COVID-19 tests following known within-school exposure.
- Proportion of exposures undergoing the test-to-stay protocol that result in additional transmission.
- Time to test positivity among those exposed to SARS-CoV-2 and undergoing the test-to-stay protocol.

Secondary Endpoints:

- Secondary #1
 - Proportion of students with positive COVID-19 test following known within-school exposure.
 - Proportion of staff with positive COVID-19 tests following known within-school exposure.
 - Proportion of exposures undergoing the test-to-stay protocol that result in additional transmission.
 - Time to test positivity among those exposed to SARS-CoV-2 and undergoing the test-to-stay protocol.
- Secondary #2
 - Proportion of students with positive COVID-19 test after indoor vs. outdoor exposure.
 - Proportion of students with positive COVID-19 test after athletic vs. classroom exposure.
 - Proportion of students with positive COVID-19 test after bus vs. classroom exposure.
- Secondary #3
 - Total number of school days missed due to symptoms after exposure.
 - Total number of school days missed due to isolation after positive COVID-19 test.
 - Total number of school days missed due to quarantine after SARS-CoV-2 exposure.

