1.5 Primary Analysis

- Objective: The proportion of students/staff with positive COVID-19 test following known within-school exposure and the proportion of exposures undergoing the test-to-stay protocol that result in additional transmission will be summarized overall, by student or staff, by school district, by school level.
 - To account for the within-school correlation of outcomes, 95% CI will be estimated for the proportion using a generalized estimating equations approach using a working independence correlation structure (Zeger et al. 1988).
 - Objective: Days to test positivity among those exposed to SARS-CoV-2 and undergoing the test-to-stay protocol will be summarized by median and interquartile ranges and nonparametric estimate of test positivity probability will be plotted.

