2.8 Sensitivity Analysis

- Objective: Repeat the main analyses among study participants who had a positive test on or after the day of exposure
- Objective: Repeat the main analyses excluding athletic exposures and exposures acquired outside of school because of the higher risk of transmission previously documented in these settings.
- Objective: Broaden the main analyses for considered positives that include presumed positives, defined as those who developed symptoms but did not receive a subsequent negative test

Manuscript #3 Test-to-Stay in K-12 schools after Household Exposure to SARS-CoV-2

Date	June 14, 2022
Corresponding author	[name]; [name], BS
Lead statistician	[name]
Statistical advisor	[name]
Project leader	[name]
Target journal	TBD

History of changes

Date	Version	Summary of changes
May 6, 2022	1.0	Initial version
June 14, 2022	1.0	Clean up

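### The indoor vs outdoor contrast is planned without stratification by activity, so it may be confounded by athletic exposure, which the SAP itself treats as higher risk

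*Protocol*

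**What the plan says.** Secondary objective 2 (Protocol 2 and 8.1.2) is to characterize how exposure setting affects spread. It has three student endpoints. The first is "Proportion and number of students with positive COVID-19 test after indoor vs. outdoor exposure"; the second is "Proportion and number of students with positive COVID-19 test after athletic vs. classroom exposure"; the third compares bus with classroom. SAP 1.3 carries the first over as "Proportion of students with positive COVID-19 test after indoor vs. outdoor exposure". Indoor and outdoor are not defined, and nothing says how athletic exposures enter the first contrast.

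On data collection, the protocol synopsis says the study will document "the context of exposure (classroom, school bus, after school sporting event, lunch, etc". Protocol 5.3 adds: "Exposure details include when exposure occurred, where it occurred, and if the individual who caused the exposure was masked or unmasked". The coding of the place of exposure is not given.

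On analysis, the planned breakdowns do not include activity. SAP 1.5 says the primary proportions "will be summarized overall, by student or staff, by school district, by school level". Protocol 8.2.2 repeats the primary analysis by participant masking and then by source masking: "The primary analysis will be repeated for masked and unmasked source of exposure separately". SAP 1.6 does the same. Neither section describes an analysis for any of the three setting contrasts.

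SAP 2.8 plans a sensitivity analysis "excluding athletic exposures and exposures acquired outside of school because of the higher risk of transmission previously documented in these settings". It belongs to Manuscript #2, whose endpoints (SAP 2.4) do not include indoor vs outdoor.

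**The concern.** The three contrasts are listed side by side as if indoor/outdoor and athletic/classroom were separate questions, but they overlap. A sporting event may be indoors or outdoors, and so may lunch. A classroom or a bus is indoors by any ordinary reading and is not athletic. Classroom and bus exposures therefore dilute the athletic share of the indoor group and have no counterpart outdoors.

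Protocol 1.1.1 points the same way. It says guidance had already removed quarantine for most masked child-to-child classroom contacts, and it names athletics and busing as examples of masked exposures outside the classroom that still led to quarantine. Protocol 3.2 defines enrollment by testing done to avoid quarantine. Of those two examples, only athletics can take place outdoors.

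If outdoor exposures are more often athletic, and athletic exposures carry more risk, the crude outdoor proportion is raised for a reason unrelated to being outdoors. A real outdoor benefit could then look smaller than it is, disappear or reverse. The study is meant to inform school mitigation guidance, and this contrast would be read for that purpose.

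**Working it through.** **Inputs from the documents.** The contrast is crude, and athletic exposure is said to carry higher risk (SAP 2.8, not quantified). No sample size calculation was made (Protocol 8.3), and no positivity rate or mix of settings is given for this endpoint. There is no figure in the plan to reproduce.

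**Assumed inputs, none of them in the documents.**
- R, the athletic to non-athletic risk ratio: 1.5, 2 or 3.
- Athletic share of outdoor exposures (a_out) and of indoor exposures (a_in), in three pairings: 50%/10%, 80%/15% and 90%/10%.
- R is taken to be the same indoors and outdoors.

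**Formula.** For one binary confounder,

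crude outdoor:indoor ratio = true ratio × B, where B = (1 − a_out + a_out × R) / (1 − a_in + a_in × R).

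**Bias factor B** (also the crude ratio when being outdoors has no effect):

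| R | 50%/10% | 80%/15% | 90%/10% |
|---|---|---|---|
| 1.5 | 1.25/1.05 = 1.19 | 1.40/1.075 = 1.30 | 1.45/1.05 = 1.38 |
| 2 | 1.50/1.10 = 1.36 | 1.80/1.15 = 1.57 | 1.90/1.10 = 1.73 |
| 3 | 2.00/1.20 = 1.67 | 2.60/1.30 = 2.00 | 2.80/1.20 = 2.33 |

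**Crude ratio if the true outdoor:indoor ratio is 0.5** (B × 0.5):

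| R | 50%/10% | 80%/15% | 90%/10% |
|---|---|---|---|
| 1.5 | 0.60 | 0.65 | 0.69 |
| 2 | 0.68 | 0.78 | 0.86 |
| 3 | 0.83 | 1.00 | 1.17 |

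Seven of the nine cells still favour outdoors, though by less than the true halving. One shows no difference and one reverses. To hide a true halving completely, B must reach 2.

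**One cell in percentages.** Take an assumed 2% risk for non-athletic indoor exposure, R = 3 and shares of 90%/10%. Indoor risk is 2% × 1.2 = 2.4%. Outdoor risk is 2% × 0.5 × 2.8 = 2.8%. The crude ratio is 2.8/2.4 = 1.17, although being outdoors halves the risk within each activity.

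**No bias.** With a_out = a_in the numerator and denominator are equal and B = 1, whatever R is. Athletic exposures in both groups do not by themselves cause bias; unequal shares do.

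**Wider ranges.** Let a_out run from 10% to 90%, a_in from 5% to 20%, and R from 1.5 to 5. B then runs from 1.4/1.8 = 0.78 (R = 5, shares 10%/20%) to 4.6/1.2 = 3.83 (R = 5, shares 90%/5%). If the indoor group were the more athletic one, the bias would favour outdoors.

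**The case against.** A reader might infer that the contrast mainly measures sport, or that indoor/outdoor cannot be separated from the recorded contexts. The documents support neither. They give no athletic share for either group, and SAP 2.8 puts no figure on the athletic risk. The context list is illustrative and open-ended, the place of exposure is collected for each participant, and the data form is not among the documents. Cross-classification may already be possible; the plan simply does not commit to it.

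The endpoint is also descriptive: a proportion and a number by setting, with no test and no power claim. Athletic vs classroom is reported beside it, so a reader would see some of the athletic gradient. Exploratory subgroup analyses are allowed. Activity is not the only possible confounder either, since masking, age and vaccination may also differ by setting.

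Much of this stands. It limits the point to possible confounding of unknown size. It does not remove the point, because the objective is worded as an effect of setting. An athletic vs classroom figure does not show how athletic exposures divide between indoors and outdoors, and an optional subgroup analysis commits to nothing. The other possible confounders are a reason for cautious wording of the result, not for ignoring the one that the SAP names.

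**Conclusion.** The point holds as possible confounding. The plan commits to a crude indoor vs outdoor contrast and leaves out a factor that its own SAP treats as raising risk. Unequal athletic shares are likely from the structure of the exposure contexts, but the documents do not show them.

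Under the assumed athletic risk ratios (1.5 to 3) and the three pairings of shares, the outdoor:indoor ratio is inflated 1.19 to 2.33 times, and a true ratio of 0.5 would appear as 0.60 to 1.17. Loss or reversal of the benefit occurs only at R = 3 with 80% to 90% of outdoor exposures athletic. With equal shares the bias is nil. These figures show what the crude contrast could hide; they do not estimate what it will hide.

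**What to change.** In SAP 1.3 and 1.6:

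1. Define indoor and outdoor, and code them separately from activity (classroom, bus, athletic, lunch, other). Derive the code from the recorded place of exposure, or use a dedicated field if that is not enough. State how many exposures cannot be classified, because the SAP's general rule drops unknown values from denominators.
2. Cross-tabulate indoor/outdoor with activity.
3. Report indoor vs outdoor within athletic and within non-athletic exposures, beside the crude figure.
4. If a combined estimate is given, take it from the plan's GEE clustered by school, with athletic/non-athletic as a term. A standard Mantel-Haenszel interval would ignore the within-school correlation that the plan otherwise allows for.

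The cost is one recoded or added field, one table and a few sentences in the SAP. The outdoor non-athletic cell may be small, so its interval may be wide and a combined model may be unstable. The table would then show readers that the data can say little about being outdoors apart from sport. Some mixing also remains within the non-athletic stratum, where the indoor side includes classroom and bus and the outdoor side cannot.
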